[Part 2 of 2 of the document. The other parts are not shown.]

Fasting blood samples (≥ 6 hours) for measurement of 5-HIAA in plasma will be collected and analyzed by a specialty laboratory. All sample processing information will be supplied by the laboratory in a separate document/study manual. Efforts should be made to schedule these visits in the morning, with instructions to the patient to arrive in a fasted state and not dose prior to the blood draw.

8.2.4 Safety Assessments

In addition to the clinical laboratory assessments described in [Section 8.2.2](#), monitoring of AEs is also considered a safety assessment and is described in detail in [Section 9](#). Clinically significant changes compared with Baseline findings for these variables should be reported as AEs on the CRF. Clinically significant changes compared with Baseline values, which are determined to be AEs, should be followed until the event has resolved, the condition has stabilized, etiology of the event is determined to be not related to study drug, or the patient is lost to Follow-up.

8.2.4.1 Vital Sign Measurements

Measurement of vital signs will include assessment of blood pressure, respiratory rate, pulse rate, and oral temperature. Vital sign measurements should not be conducted within the 30 minutes immediately following any phlebotomy.

Efforts should be made to standardize blood pressure collection across all patients and visits. Patients should be seated for at least 5 minutes prior to collection. All measurements should be assessed on the same arm, and by the same technician where possible.

Additional measurements may be obtained if clinically indicated. Vital sign measurements will be measured as indicated in [Appendix A](#).

8.2.4.2 Physical Examinations

Complete physical examinations will be performed as outlined in [Appendix A](#). Complete physical examinations will include a minimum of a review of the patient's general appearance, head, eyes, ears, nose, and throat (HEENT), neck, heart, lungs, abdomen, back and extremities, skin, and general neurological system.

Symptom-oriented physical examinations will be performed at all other time points and as clinically indicated.

In addition, weight will be captured during each physical examination. Efforts should be made to standardize weight collection across all patients and visits. Patients should be instructed to remove shoes and heavy clothing (eg, heavy coats, jackets) prior to measurement. For weight collection, an effort should be made to use the same scale throughout the study where possible. In instances where multiple scales may be used, efforts should be made to reset the scale to zero prior to collection of weight measurement.

8.2.4.3 Electrocardiograms

Electrocardiograms (12-lead ECGs) will be performed as specified in [Appendix A](#).

8.2.4.4 Adverse Events of Special Interest

Monitoring of these events will be the responsibility of the DSMB. The process of data collection and assessment of the events will be detailed in a separate DSMB charter.

Additional information will be collected if episodes of any of the following AEs of special interest occur.

8.2.4.4.1 Central Nervous System Events

Central nervous system events of special interest may include any clinically significant changes in mood, physical affect, or exacerbation of preexisting CNS conditions (eg, depression, migraine headaches).

8.2.4.4.1.1 Depression Detection

Patients will be evaluated beginning at Day 1 (Baseline) and at each subsequent visit for indications of depression. During each visit the patient will first be asked to respond to the question “During the past month, have you often been bothered by feeling down, depressed, or hopeless?” Followed by “During the past month, have you often been bothered by little interest or pleasure in doing things?” A positive response prior to Day 1 dosing will be captured on the medical history CRF page. Positive responses following the first dose will be captured as an AE and will be followed as an AE of special interest.

8.3 Other Assessments

8.3.1 Chromogranin A (CgA)

Blood samples for measurement of chromogranin A (CgA) levels will be collected as indicated in [Appendix A](#).

8.3.2 Disease Progression

Data will also be collected on measures of disease progression as performed as standard of care including, but not limited to: interpretation of clinical scans (eg, PET, CAT, MRI scans of tumor), or Investigator assessment of disease status, while the patient is enrolled in the study.

8.3.3 Quality of Sleep Assessment

Quality of sleep will also be evaluated beginning Day 1 (Baseline) and at each subsequent visit thereafter. Patients will be asked to respond to the following question “Since your last visit, how many times a night (on average) do you wake up due to your CS symptoms?” based on the following scale 0, 1, 2, 3, 4, >4.

8.4 Appropriateness of Assessments

The assessments used in this study conform to the usual clinical and laboratory assessments of patients with CS participating in clinical trials and are typical of a Phase 3 study.

9.1 Adverse Events

It is the responsibility of the Investigator to document all AEs that occur during the study.

Adverse event is defined as any untoward medical occurrence associated with the use of a drug in humans, whether or not considered drug related.

Life-threatening adverse event or life-threatening suspected adverse reaction: An adverse event or suspected adverse reaction is considered "life-threatening" if, in the view of either the Investigator or Sponsor, its occurrence places the patient or subject at immediate risk of death. It does not include an adverse event or suspected adverse reaction that, had it occurred in a more severe form, might have caused death.

An AE includes any noxious, pathological, or unintended change in anatomical, physiological, or metabolic functions as indicated by physical signs or symptoms occurring in any phase of the clinical study whether or not considered related to the study medication. This definition includes an exacerbation of preexisting medical conditions or events, historical condition not present prior to study treatment, which reappear following study treatment, intercurrent illnesses, hypersensitivity reactions, drug interaction, or the significant worsening of the disease under investigation that is not recorded elsewhere in the CRF. Anticipated day-to-day fluctuations of pre-existing conditions that do not represent a clinically significant exacerbation or worsening need not be considered AEs.

Any laboratory abnormality fulfilling the criteria for a SAE (Section 9.2) should be reported as such, in addition to being recorded as an AE. Any treatment-emergent abnormal laboratory result which is clinically significant, ie, meeting 1 or more of the following conditions, should be recorded as a single diagnosis AE:

- Is considered to be an SAE,
- Results in discontinuation from study treatment, or
- Results in a requirement for a change in concomitant therapy (ie, addition of concomitant therapy)

In the event of medically significant unexplained abnormal laboratory test values, the tests should be repeated and followed up until they have returned to the normal range and/or an adequate explanation of the abnormality is determined.

TEAEs are defined as any AEs reported after the first dose of study drug on Day 1. Adverse events reported after consent of a patient, but before administration of study medication, will be reported in the Medical History.

AEs should not be solicited with leading questions that suggest specific signs or symptoms. Rather, AEs should be solicited by asking the patient a non-leading question such as: “Do you feel different in any way since receiving the dose or since the last assessment?”

The Investigator will evaluate all AEs with regard to the maximum intensity and relationship to study drug, as follows:

- Maximum intensity

Maximum intensity should be assigned using 1 of the following 3 severity grades:

- Mild: aware of event but easily tolerated
- Moderate: discomfort, enough to cause interference with usual activity
- Severe: incapacitating: patient unable to work or perform usual activities

- Relationship to study drug

Not related:

- Does not follow a reasonable temporal sequence from administration of the drug
- Could be reasonably explained by other factors, including underlying disease, complications, concomitant drugs, or concurrent treatment.

Possibly related:

- That follows a reasonable temporal sequence from administration of the drug (including the course after withdrawal of the drug), or
- For which the possibility of the study drug being the causative factor (eg, existence of similar reports attributed to the suspected drug and its analogues; reactions attributable to the pharmacological effect) could not be excluded, although other factors such as underlying disease, complications, concomitant drugs, or concurrent treatment are presumable.

Probably related:

- That follows a reasonable temporal sequence from administration of the drug (including the course after withdrawal of the drug), and
- For which the possibility of factors other than the drug, such as underlying disease, complications, concomitant drugs, or concurrent treatment, could not be excluded as the cause.

Definitely related:

- Follows a clear temporal sequence from administration of the study drug.
- Could not be possibly explained by the known characteristics of the patient's clinical state, environmental or toxic factors, or other modes of therapy administered to the patient.
- Disappears or decreases on cessation or reduction in dose of the study drug.
- Reappears or worsens when the study drug is re-administered.
- Follows a response pattern known to be associated with administration of the study drug.

The degree of certainty with which an AE is attributed to treatment with study medication (or alternative causes, eg, natural history of the underlying diseases, concomitant therapy, etc.) will be determined by how well the event can be understood in terms of known pharmacology of the study medication and/or reaction of similar nature being previously observed with the study medication or the class of study medication.

All AEs should be followed for at least 30 days following the last dose of study drug or until the event has resolved, the condition has stabilized, or the patient is lost to Follow-up. For each patient for whom an AE was reported that did not resolve before the end of the reporting period, Follow-up information on the subsequent course of events must be submitted to the Sponsor. This requirement indicates that follow-up may be required for some AEs after the patient has completed his/her participation in the study

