10.4.2.1 Adverse Events

All AEs will be coded and listed by body system and preferred term based on the Medical Dictionary for Regulatory Activities (MedDRA). Summaries using descriptive statistics will be provided for treatment-emergent AEs, drug-related AEs and AEs by intensity. Treatment-

emergent AEs are those events not present at Baseline, but occurring after the start of study drug, or if existing at Baseline, increasing in intensity after initiation study drug. Summaries made by intensity will select the event with the highest intensity when multiple occurrences of the same event are reported for the same patient. In a similar manner, summaries prepared by drug relationship will select the event with the greatest degree of relationship when a study reports multiple occurrences of the same event. On-study deaths will be reported for deaths occurring during the active phase of the treatment period and 30 days after stopping study drug. Also, deaths occurring outside the 30-day window, but secondary to an AE reported within the 30-day post treatment period, will be reported as well.

Listings will be provided for deaths, SAEs, and discontinuations due to AEs. Additional summaries or listings of AEs may also be provided.

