5.1 Overall Study Design

The study will be conducted as a multicenter, open-label, long-term extension study to further evaluate long-term safety and tolerability of telotristat etiprate.

Patients currently participating in any LX1606 Phase 2 CS study may enter into this extension study upon institutional or local approval of the protocol. Patients participating in a Phase 3 CS study may enter into this extension study at the Week 48 visit. All patients who enter into this extension study will be exempt from any follow-up visit required by the original study and will not experience an interruption in study drug due to the transition from the original protocol to LX1060.1-302-CS.

Following confirmation of eligibility, patients will complete a series of visit assessments in order to establish Baseline symptoms. Patients will then continue on open-label LX1606 at the same dose level identified in the original study.

Downward dose adjustment will be permitted during the study if evidence of intolerability emerges. Patients who experience intolerability at the 250 mg tid dose level must be discontinued from the study. Patients may return to the previous dosing at the discretion of the Investigator and in consultation with the Medical Monitor.

Upon completion or early withdrawal from treatment, all patients will be required to complete a 14-day Follow-up Period, during which no study drug will be administered.

A Data Safety Monitoring Board (DSMB) will review safety data quarterly throughout the study.

6. Study Population

Adult patients who are currently participating in ongoing Phase 2 or Phase 3 telotristat etiprate CS clinical protocols will be enrolled into the study. Up to 100 patients are expected to enroll in this study. Approximately 70 sites worldwide will participate in the study. Patients may continue allowed medications as background therapy provided they remain on stable-doses throughout the Treatment Period.

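### As Section 9.1 words the causality scale, an adverse event with all other causes excluded but no re-administration falls to Possibly related, below an event with weaker evidence

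*Protocol*

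**What the plan says.** Section 9.1 has the investigator grade each AE as Not, Possibly, Probably or Definitely related. The two Possibly bullets are joined by *or* and the two Probably bullets by *and*. The five Definitely bullets have no connector:

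1. "Follows a clear temporal sequence from administration of the study drug"
2. no possible explanation from the patient's clinical state, environmental or toxic factors, or other treatment
3. "Disappears or decreases on cessation or reduction in dose of the study drug"
4. "Reappears or worsens when the study drug is re-administered"
5. "Follows a response pattern known to be associated with administration of the study drug"

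Neither criterion 3 nor criterion 4 is limited to cases where the drug was in fact stopped, reduced or given again.

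A later paragraph of Section 9.1 bases the degree of certainty on how well the event fits the drug's known pharmacology and/or a "reaction of similar nature being previously observed with the study medication or the class of study medication". It does not mention re-administration.

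Section 10.4.2 plans a summary of treatment-emergent AEs by relationship. Section 10.4.2.1 adds that, for repeated occurrences of the same event, that summary "will select the event with the greatest degree of relationship".

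**The concern.** A causality scale should be monotone: better evidence for the drug should never lower the grade. Here the top grade appears to depend on things that often cannot be observed. After a permanent stop there is no re-administration, and after a death there is neither improvement nor re-administration. A toxicity not seen before has no known pattern. The study's primary objective is long-term safety and tolerability, so these are events it particularly needs to grade well.

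The missing connector also matters in itself. With approximately 70 sites planned, investigators may differ on whether the five bullets are a checklist or features to be weighed. The grade is assigned at data capture, so a later analysis plan cannot repair it.

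**Working it through.** No arithmetic applies, and the protocol states no figure on this point. The check is logical and uses the numbering of the five criteria above.

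**Step 1: which connector?** If any one criterion were enough, clear timing alone would earn the top grade. That would place it above Probably, which needs two conditions, and would leave the middle grades almost empty. Requiring all five is the natural reading, though it is an inference.

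**Step 2: what do the lower grades need?** Probably needs reasonable timing *and* other causes that could not be excluded. Possibly needs reasonable timing *or* a drug cause that could not be excluded.

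**Step 3: run cases through the scale as written.**

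| Case | 1 Timing | 2 Others excluded | 3 Improves on stopping | 4 Returns on re-administration | 5 Known pattern | Grade |
|---|---|---|---|---|---|---|
| A. Resolves on stopping, drug never given again | yes | yes | yes | not observable | yes | Possibly |
| B. Weaker evidence | reasonable | no | any | any | any | Probably |
| C. Fatal or irreversible occurrence | yes | yes | no | not observable if fatal | yes | Possibly |
| D. New toxicity with positive response to both challenges | yes | yes | yes | yes | no | Possibly |
| E. Abates on reduction, recurs on resumption, then ends treatment | yes | yes | yes | yes | yes | Definitely |

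Case A fails Definitely on criterion 4. It then fails Probably *because* other causes were excluded, and it enters Possibly through that grade's timing bullet. Cases C and D follow the same route, failing Definitely on criterion 3 (and 4 if fatal) and on criterion 5 respectively. Case B has less evidence than A and sits one grade higher. The scale is therefore not monotone.

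**Step 4: compare with the general paragraph.** Under the pharmacology and/or prior-reaction rule, a never-observed event that the pharmacology explains could carry high certainty. Criterion 5, read as required, excludes it. The two parts of Section 9.1 do not agree.

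**Step 5: where does the grade go?** It enters the relationship summaries of Sections 10.4.2 and 10.4.2.1. Reporting under Section 9.2 covers any SAE, and Section 9.3 works from a reasonable possibility of causation. Neither depends on the top grade.

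**The case against.** The best defence is that nothing in Section 9.1 says all five criteria are required. They could be features weighed under the general paragraph, which looks to pharmacology and/or precedent. That is a fair reading, but it leaves a top grade with no stated rule beside two grades whose connectors are explicit. It also leaves the wording of Probably untouched.

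The second defence is that little turns on it. AEs leading to discontinuation, SAEs and deaths are summarized or listed whatever their grade, and no stopping rule shown uses the top grade. This stands, and it limits the point to the split by grade.

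Stronger readings are tempting but not supported:

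- *No AE that ends treatment can be Definitely related.* A reader might infer this from Section 5.1 of the Amendment 1 text: "Patients who experience intolerability at the 250 mg tid dose level must be discontinued from the study". But Sections 5.1 and 7.4 of that text also allow reduction and return to the previous dose, and Section 7.4 allows interruption. Case E can therefore arise before final discontinuation. Only AEs with no re-exposure are barred. Those sections of the latest version were not available for this review, and the point does not depend on them.
- *The top row can hold only mild events.* Nothing ties interruption or resumption to intensity.
- *The general paragraph reinforces the bar on new toxicities.* Its reference to pharmacology and its and/or loosen criterion 5.

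**Conclusion.** The point holds as a defect of classification. On the all-five reading, cases A, C and D are shut out of the top grade and fall two grades to Possibly related, below an event whose alternative causes remain open. How many events would move cannot be estimated from the protocol.

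The conclusion rests on two assumptions. The first is that all five criteria are required; if they are not, the fault becomes an unspecified rule for the top grade, and the ordering problem in Probably remains for any event not judged Definitely. The second concerns the drug-related total, which is unchanged provided that drug-related means Possibly or higher. That is the usual meaning, but the protocol text shown does not define it.

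The change is worth making because the rule misorders evidence in a planned safety table and is cheap to correct. It does not call expedited reporting or the capture of discontinuations and deaths into question.

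**What to change.** Edit Section 9.1 and the case report form guideline as follows:

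- State the connector for Definitely related: all criteria that apply must be met.
- Qualify criterion 3: *if the drug was stopped or reduced and the event is reversible*. The second condition is needed so that fatal and irreversible events are not excluded.
- Qualify criterion 4: *if the drug was re-administered*.
- Make known response pattern supportive rather than required, in line with the general paragraph.
- Add a second limb to Probably related, for example: *or other factors have been excluded but an applicable Definitely criterion is not met*. Excluding other causes then no longer lowers the grade.

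This changes classification only. It asks for no re-administration and no change in patient management.

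Apply the revised scale to all events, or prospectively with the change date flagged in the summaries. Do not regrade only events that led to discontinuation or death: selecting by outcome in an open-label study would make grades non-comparable across events. The cost is one text edit plus either some regrading work or a flagged change of scale.

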9.2 Serious Adverse Events (SAEs)

An SAE is defined as any event that results in any of the following outcomes:

1. Death
2. A life-threatening adverse event;
3. Inpatient hospitalization or prolonging of an existing hospitalization (see [Section 9.2.1](#) for information on hospitalization as an SAE);

4. A persistent or significant incapacity or substantial disruption of the ability to conduct normal life functions; or
5. A congenital anomaly/birth defect.

Important medical events that may not result in death, be life-threatening, or require hospitalization may be considered serious when, based upon appropriate medical judgment, they may jeopardize the subject and may require medical or surgical intervention to prevent one of the outcomes listed above.

Any SAE must be reported by telephone or facsimile within 24 hours of discovery of the event. Investigators should not wait to receive additional information to fully document the event before notifying the Sponsor of an SAE at:

Sites in North America must report to:

Safety Data [contact]

Safety [contact]

Email address (in case of fax failure): [contact]

Sites outside North America must report to the country specific toll-free fax numbers identified below:

Australia: [REDACTED]
Belgium: [REDACTED]
Brazil: [REDACTED]
France: [REDACTED]
Germany: [REDACTED]
Israel: [REDACTED]
Italy: [REDACTED]
Netherlands: [REDACTED]
Spain: [REDACTED]
Sweden: [REDACTED]
United Kingdom: [REDACTED]

Email Address (in case of fax failure): [REDACTED]

The telephone report should be followed by full written summary detailing relevant aspects of the SAE in question using the provided SAE report form. Where applicable, information from relevant hospital case records and autopsy reports should be obtained. The SAE should also be recorded on the AE page of the patient's CRF.

An SAE that occurs after completion of the study but, in the opinion of the Investigator, is related to the study medication, should be reported as described for an SAE. If an AE does not meet the regulatory definition of "serious" but is considered by the Investigator to be

related to the study medication and of such clinical concern as to influence the overall assessment of safety, it must be reported as defined for an SAE.

All patients (including discontinued patients) with a SAE must be followed until the event resolves or reaches a new Baseline, but for a minimum of 30 days after the last dose of study drug.

